6.1. Randomisation and Blinding

Random assignment of subjects will be done using the randomizer found in the web (www.Randomizer.org/form.htm). A non-team member will generate the randomized allocation sequence, seal the group numbers in individual envelopes, and arrange them according to the randomized allocated sequence. These envelopes will be kept under lock and key in TTSRHC. The same non-team member will pass these sealed envelopes in accordance to the randomized allocated sequence one at a time to the CPI who will enrol and assign the eligible subjects to their groups. The unmasking of the randomization will be at the end of data collection and fMRI analysis. A blinded assessor will perform all the clinical assessments. The I2R who will be performing the fMRI analysis will be blinded to the group which the subjects are in.

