3. STUDY POPULATION

3.1. List the number of subjects to be enrolled.

20 subjects will be randomly assigned to a control (N=10) and experimental group (N=10). 4 normal healthy subjects will also be recruited for fMRI investigations.

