3.3. Inclusion Criteria

All patient subjects have to fit in the following Inclusion criteria to be included in the study: diagnosis of stroke due to infarct resulting in UL hemiparesis (with confirmation from MRI and Computed axial tomography (CT) scans); and admitted within first 21days post-stroke in TTSHRC with Montreal Cognitive Assessment (MoCA) score ≥ 19 . In addition, stroke subjects with positive motor evoked potential (MEP +ve) and with severe to moderate UL paresis (Upper Limb Fugl Meyer (ULFM) score below or equal to 50) admitted to TTSHRC will be selected. Subjects with severe and moderate UL paresis are selected because based on clinical observation subjects with this level severity require intensive UL practice to improve their UL functions, while subjects with mild paresis do not require such high intensity of UL practice for significant improvement. Investigation of motor evoked potential on extensor carpi radialis on the affected hand will be performed in NUH on stroke patients using a single Magstim 200 to prognosticate recovery. Subjects with MEP +ve will be selected to ensure that all the subjects chosen in this study have intact ipsilesional cortical spinal tract function to make comparison of UL recovery more consistent.

All normal healthy subjects aged 21 years old and above who are able to give informed consent and follow commands will be recruited.

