5. STUDY DESIGN

Experimental procedure

The subjects will be randomly assigned to a control (N=10) and experimental group (N=10).

Experimental Group

The experimental group will receive one **SURE** program booklet with specific instructions and pictorial illustrations of each exercise and functional use according to their affected ULFM score. There are 3 booklets available (Level 1A for patients with affected ULFM score from 0 to 10; Level 1B for patients with affected

ULFM score from 11 to 22; Level 2 for patients with affected ULM score from 23 to 50). Each **SURE** program booklet consists of stretching exercises, strengthening exercises and performance of simple motor tasks such as reaching, picking up cubes etc. Each exercise will be graded and progressed according to the subjects' affected UL capability by the Clinical Principal Investigator (CPI) who is an experienced principal physiotherapist. The **SURE** program booklet also consists of selected motor tasks to be performed by the subjects using their affected UL. Functional activities such as subjects will be using their affected UL to wipe their faces; wiping the table after eating; applying lotion by the affected hand along the unaffected arm and legs after shower; drinking water from cup/ bottle; lifting and placing affected hand on table top; etc. Each functional motor task will be selected, graded and progressed by the PI according to the subjects' affected UL motor capability during the reviews. The subjects will be taught how to perform the exercises and functional tasks during the first session. The performance of the exercises and functional motor tasks will be reviewed by the CPI three times per week for the first 2 weeks, two times for the third week and one time for the fourth week of intervention period.

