6. METHODS AND ASSESSMENTS

Outcome Measures

UL functional outcome measures

UL Fugl Meyer Scale (ULFM)

UL Fugl Meyer Scale will be used to stratify subjects to their level of UL severity and assessment of UL impairment. ULFM score can be subdivided into 3 categories to define the different level of severity of paresis (severe= 0 to 22; moderate=23 to 50; mild>= 51). ULFM will be one of the primary outcome measures to determine UL recovery.

Action Research Arm Test (ARAT)

ARAT will be used as the primary outcome measure of UL functional outcome. ARAT will be one of the primary outcome measures to determine UL recovery.

Measure of UL practice and use

Rating of Everyday Arm-use in the Community and Home (REACH Scale)

The REACH scale is a self-report measure that captures how much an individual with stroke use affected UL outside clinical setting. It has one scale for subjects whose dominant UL is affected and another scale for subjects whose non-dominant UL is affected. It will be used to rate patients' affected UL use after discharge.

Measure of UL practice and use using accelerometry

One tri-axial accelerometer (ActiGraph GT3X+, ActiGraph LLC, Pensacola, Florida) will be placed on subject's unaffected wrist to establish the duration of unaffected UL use in the ward for 3 days in the first week. Another tri-axial accelerometer will be placed on subject's affected wrist for 3 weekdays each week of the 4-week intervention period to assess the amount of affected UL use. The accelerometers will be worn by all subjects (both experimental and control groups) from 8am to 8 pm on the day of donning.

Measures of feasibility of accelerometry in measuring affected UL use

The compliance rate of wearing the accelerometers during the 4 weeks of intervention period will be used to assess compliance. Subjects will also be asked to fill a questionnaire to rate the acceptance, ease, comfort, discomfort, benefits, and problems of wearing the accelerometers in the ward.

*Measures of **SURE** program's feasibility*

The key measure of **SURE** program's feasibility will be the additional affected UL practice and use per day as measured by the accelerometers.

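### Section 6 says ULFM will be used to stratify subjects by severity, but neither the allocation in Section 6.1 nor the between-group test in Section 11.2 takes severity into account, so the sections need reconciling

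*Protocol*

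**What the plan says.** Section 6 of the protocol (Methods and Assessments, ULFM entry) states that "UL Fugl Meyer Scale will be used to stratify subjects to their level of UL severity and assessment of UL impairment". It gives the bands as "severe= 0 to 22; moderate=23 to 50; mild>= 51" and adds that "ULFM will be one of the primary outcome measures to determine UL recovery". Section 3.3 admits patients with "severe to moderate UL paresis (Upper Limb Fugl Meyer (ULFM) score below or equal to 50", so only the severe and moderate bands can occur.

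Section 3.1 fixes the numbers: "20 subjects will be randomly assigned to a control (N=10) and experimental group (N=10". The allocation procedure is in Section 6.1: "Random assignment of subjects will be done using the randomizer found in the web". It continues: "A non-team member will generate the randomized allocation sequence, seal the group numbers in individual envelopes, and arrange them according to the randomized allocated sequence". That is one sequence and one ordered set of envelopes. No strata or blocks are named.

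The only place where the ULFM level is put to use is Section 5, where experimental subjects receive a booklet "according to their affected ULFM score. There are 3 booklets available" (bands 0-10, 11-22 and 23-50).

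Section 11.2 compares upper-limb outcomes between the groups at each of five time points with a Wilcoxon test at p<0.05. It names no severity band and no baseline score.

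**The concern.** A reader of Section 6 would expect severity to be controlled somewhere. Section 6.1 does not do it by design, and the test in Section 11.2 does not do it in analysis. The allocation part cannot wait for a statistical analysis plan: strata must exist before the first envelope is sealed, and a later plan can adjust for an imbalance but cannot remove it.

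The point matters here because ULFM is both the severity measure and a primary outcome. A subject who enters in the severe band will tend to have a lower ULFM afterwards, whatever the arm. With 10 subjects per arm, an uneven severity split carries directly into an unadjusted comparison at each visit.

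**Working it through.** The protocol gives no imbalance probability, power, effect size or SD, since N=10 per arm rests on feasibility (Section 11.1). There is therefore no figure of its own to reproduce.

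**Inputs.** From the protocol: 20 patients, arms fixed at 10 and 10 (Section 3.1); bands 0-22 and 23-50 (Sections 3.3 and 6). Assumed: the number K of severe patients, which the protocol does not give.

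**Chance of a severity imbalance.** With fixed arms, the number x of severe patients in one arm is hypergeometric:

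P(x) = C(K,x) C(20-K,10-x) / C(20,10), with C(20,10) = 184,756.

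For K = 10, a 7:3 or worse split in either direction:

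2 × (120² + 45² + 10² + 1²) / 184,756 = 2 × 16,526 / 184,756 = 0.179. In one given direction it is 0.089.

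For other mixes, the comparable event is that severe counts differ by 4 or more between arms:

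| Severe patients (K) | Allocations out of 184,756 | Probability |
|---|---|---|
| 10 | 33,052 | 0.179 |
| 9 or 11 | 12,892 | 0.070 |
| 8 or 12 | 31,372 | 0.170 |
| 7 or 13 | 10,582 | 0.057 |
| 6 or 14 | 26,026 | 0.141 |
| 5 or 15 | 6,006 | 0.033 |
| 4 or 16 | 16,016 | 0.087 |

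For odd K the difference is odd, so 4 or more means at least 5; a difference of 3 or more has probability 0.30-0.37 there. If each patient's severity is random, the chance is 0.115 at p = 0.5 and 0.085 at p = 0.3 or 0.7.

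**Size of the baseline gap (illustrative).** Band mid-points are (0+22)/2 = 11 and (23+50)/2 = 36.5. A 7:3 split gives

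- arm with 7 severe: 0.7 × 11 + 0.3 × 36.5 = 18.65
- arm with 3 severe: 0.3 × 11 + 0.7 × 36.5 = 28.85
- gap: 10.2 points.

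**What this does to the comparison (illustrative simulation).** Assumptions: no treatment effect, K = 10, baseline uniform within each band, the same mean gain in both arms with SD 5 or 10, and an unadjusted two-sample rank test on the later score. (Section 11.2 names the signed-rank test, but the comparison is between groups, so the rank-sum version was used.) The test rejects in under 1% of trials at a 5:5 split, about 14-15% at 7:3 and about 46-66% at 8:2. At 7:3 and 8:2, every rejection favours the arm with fewer severe subjects. Weighted by the probability of each split, overall rejection is about 4%. With SD 10, for splits 5:5 to 9:1: 0.344 × 0.004 + 0.477 × 0.019 + 0.156 × 0.137 + 0.022 × 0.469 + 0.001 × 0.859 ≈ 0.043. The overall error rate holds; the error rate given the split that actually occurs does not.

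**The case against.** The strongest answer is that stratify in Section 6 simply means classify. The sentence sits under outcome measures, does not mention randomisation, and is followed by the cut-offs. The booklets in Section 5 share the 22/23 cut. This stands as a possible reading. A reader might infer that the protocol promises stratified randomisation and then breaks the promise; the text does not support that. But the booklets use three bands and concern one arm only, whereas Section 6 speaks of subjects in general. Under the classify reading, severity is still left out of both the allocation and the stated test.

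A second answer is that randomisation already allows for chance imbalance. That is right: a reader might infer a raised false-positive rate, and there is none overall. The loss is in precision and in reading the one result obtained.

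Third, a reader might take the 18% as a property of the trial. It depends on an even mix that the protocol does not give, and it is the highest value over the mixes tried. Nor is the 17% for 8 severe subjects a 7:3 split; it is 6:2 or worse.

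Fourth, a reader might call ULFM severity the strongest prognostic factor. No section ranks it so. Section 1.1 cites motor evoked potentials and corticospinal fractional anisotropy as predictors, and Section 3.3 limits entry to MEP-positive patients with ULFM of 50 or less, which already narrows the range.

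Finally, the trial is an exploratory pilot, covariates may be set out in an analysis plan not shown, and Section 11.2 also compares the groups before intervention, so an imbalance would be seen. These points lower the weight. They do not remove it: effectiveness is a primary objective (Section 2.2), tests are made at p<0.05, and seeing an imbalance is not the same as adjusting for it.

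**Conclusion.** The point holds as an unresolved ambiguity with a modest statistical cost. Section 6 speaks of stratifying by ULFM, Section 6.1 fixes one sequence without strata, and the test in Section 11.2 carries no severity or baseline term. That the list is unstratified is inferred from the single sequence; the protocol does not say so outright.

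The size is conditional: an 18% chance of a 7:3 or worse split with 10 severe and 10 moderate subjects in fixed arms of 10, and about 3-18% for a difference of 4 or more over mixes from 4 to 16 severe. The gap of about 10 ULFM points assumes that every subject sits at a band mid-point. This is a worthwhile improvement and not a flaw that invalidates the trial.

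**What to change.** 1. **Analysis.** In Section 11.2, replace the unadjusted per-visit comparison of ULFM and ARAT with one that accounts for baseline severity, for example a stratified rank-sum (van Elteren) test by ULFM band, or a rank ANCOVA on the baseline score. Fix the choice before unmasking. Baseline ULFM and ARAT are already collected, so this costs almost nothing.

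2. **Wording and allocation.** Reconcile Sections 6 and 6.1 in one of two ways:
   - Have the same non-team member prepare two envelope sequences, for ULFM 0-22 and 23-50, with randomly mixed block sizes not disclosed to the enrolling investigator. ULFM is needed for eligibility, so the band is known before allocation. Severe counts would then differ by at most 1 with blocks of 2, or at most 2 with blocks of 4, barring replacements (Section 3.6) and allocation errors.
   - Or state in Section 6 that ULFM only classifies subjects and is not a stratification factor for randomisation.

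The first option costs a second stack of envelopes before enrolment. Arms may end slightly unequal, for example 11/9. Small blocks also carry some predictability, because the enrolling investigator knows the group assignments (Section 8.5). That makes the stratified list the more debatable part; the adjusted analysis is worth making under either option.

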6.2. Contraception and Pregnancy Testing

Although MRI is a non-invasive and non-radioactive imaging technology and is not known to affect baby's development, it is prudent to exclude pregnant women. If the subject become pregnant during this study, she must stop participating and call your doctor or the Principal Investigator immediately.

6.3. Study Visits and Procedures

a. *Screening Visits and Procedures*

CPI will identify patients that will be admitted to TTSHRC based on their medical records based on the study's patients' inclusion and exclusion criteria. Once the CPI check that the particular patient meets all the inclusion's criteria, she will then approach the patients' therapist to confirm that patient's eligibility for the recruitment to the study. In addition, the CPI will also check with the treating doctor to find out if that patient is medically fit and stable to travel to CIRC and back. Once the treating therapist confirms that that particular patient meets the study inclusion's criteria and the treating doctor confirms that the patient is medically fit and stable for the travel, the patient will then be approached to invite to participate in the study. If that patient agrees to participate in the study, he/ she will have to sign informed consent, and complete a pre-intervention clinical assessment and a fMRI investigation before the commencement of the study's intervention.

b. *Study Visits and Procedures*

	Clinical Assessments (TTSHRC)/ no. of visit	TMS Screening (NUH)/ no. of visit	fMRI Investigations (CIRC@NUS)/no. of visit
Pre-Intervention	1 (Inpatient)	1 (Inpatient)	1 (Inpatient)
Two weeks after start of Intervention	1 (Inpatient)	NIL	NIL
Post-Intervention	1 (In/ Outpatient)	NIL	1 (In/ Outpatient)
One Month Post-Intervention	1 (Outpatient)	NIL	NIL
Three Months Post-Intervention	1 (Outpatient)	NIL	1 (Outpatient)

4 weeks of **SURE** program intervention will start continuously after pre-intervention TMS screening, clinical assessment and fMRI investigation.

The CPI who has successfully completed all the prescribed requirements of the CPR + AED Course will accompany the inpatient subjects to NUH and CIRC at NUS for TMS screening and fMRI scanning in ambulance from TTSHRC and back to TTSHRC to ensure safety of the subjects during transit for TMS screening and fMRI scanning.

The CPI following the subjects to and back from NUH and CIRC will follow the routine inter-institution transportation protocol for patients with AWAS 0- 1 (see attached document: JCI-ACC-HAP-008.doc).

Before any TMS and fMRI appointment is made, the CPI will check with the treating doctor if the subject is clinical fit to travel, if the doctor deems the subject clinically unfit to travel, no TMS or fMRI appointment will be made.

On the day of travel, the CPI will check with the treating doctor if the subject is clinical fit to travel, if the doctor deems the subject clinically unfit to travel, the ambulance services and TMS/ fMRI will be cancelled for that day and the subject will remain in the ward and not travel. If the doctor deems the subject clinically stable to travel, the subject will be accompanied by CPI and paramedic in the ambulance service to NUH and CIRC.

In the process of transportation, if the subject suffers any adverse events or re-stroke, the paramedic accompanying the subject in the ambulance will manage the emergency situations and send the subject to the nearest hospital Emergency Department. The CPI will call the treating doctor in TTSHRC to inform and update on the emergency situation and subject's location. The CPI will stay with the subject until further instructions has been given by the treating doctor in TTSHRC.

c. *Final Study Visit:*

The final study visit will be either the three-months post-intervention clinical assessment or fMRI investigation.

d. *Post Study Follow up and Procedures*

CPI will check on all clinical assessments and TPI will check on all fMRI investigations to ensure that all the assessments and investigations are done accurately and the results obtained are accurately. CPI and TPI will also check and monitor for any adverse events occurring during **SURE** program and fMRI investigations.

e. *Discontinuation Visit and Procedures*

All clinical assessments and fMRI investigations should be done until the subject indicate to the CPI that he/she want to withdraw voluntarily from participation in the study at any time. Subjects may also withdraw voluntarily from receiving the **SURE** program for any reason. All the withdrawals and reasons for withdrawal will be evaluated to gain an insight to the feasibility of SURE program. As **SURE** program is a safe exercise program, no efforts will be made to follow-up if the subject chooses to withdraw from the program, unless subject has specifically requested for follow-up.

7. TRIAL MATERIALS

NIL

7.1. Trial Product (s)

NIL

7.2. Storage and Drug Accountability

NIL

8. TREATMENT

8.1. Rationale for Selection of Dose

Exercise Dosage of **SURE** Program

The subjects will perform the self-exercises for 60 minutes (3x 10-20 minutes) and functional tasks (as and when it is required in the subjects' daily function) per day for 6 days per week in the ward throughout the 4 weeks intervention period. These exercises are performed in addition to daily therapy. Additional period of self exercises and affected UL's functional use are performed in the ward to increase the dosage of affected UL activity as studies have found that amount of affected UL activity during therapy session are limited. Additional of 1 hour of affected UL activity (total of additional of 24 hours for intervention period) was chosen to enhance affected UL recovery

See Appendix 1 to see details of **SURE** program booklet

8.2. Study Drug Formulations

NIL.

8.3. Study Drug Administration

NIL.

8.4. Specific Restrictions / Requirements

NIL

8.5. Blinding

The therapists performing the clinical assessments, the I2R and CIRC scientists performing the fMRI investigations and analysis will be blinded to which group the subjects are in. Only the CPI and another team member who will be carrying out the **SURE** program when PI is unavailable will know which group the subjects are in. The subjects will not be told which group they are in as well. The **SURE** program and education program will be delivered to them without disclosing which group they are in. The unblinding is expected and will only occurs after all the clinical assessments and fMRI investigations are completed for individual subjects.

8.6. Concomitant therapy

Conventional therapy which occurs from Monday to Friday which includes approximately 45 minutes of physiotherapy and 45 minutes of occupational therapy daily in TTSHRC.

9. SAFETY MEASUREMENTS

9.1. Definitions

- UPIRTSO Events
Occurrence of epileptic seizures during fMRI investigations
- Serious Adverse Events
MRI related injury or death arising from the action of the strong magnetic field on any metal objects on or within the body
- Other adverse Events
MRI related burns and electric shocks
Development of allergy to the straps of the accelerometers

9.2. Collecting, Recording and Reporting of “Unanticipated Problems Involving Risk to Subjects or Others” – UPIRTSO events and “Serious Adverse Events” (SAEs) to the NHG Domain Specific Review Boards (DSRB)

Reporting Timeline for UPIRTSO Events and SAE to the NHG DSRB:

1. **Urgent Reporting:** All problems involving local deaths, whether related or not, should be reported immediately – within 24 hours after first knowledge by CPI.
2. **Expedited Reporting:** All other problems must be reported as soon as possible but not later than 7 calendar days after first knowledge by CPI.

9.3. Collecting, Recording and Reporting of "Serious Adverse Events" (SAEs) to the Health Science Authority (HSA)

NA

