To fill the gaps in knowledge of early UL practice, the understanding of the neuro-biological mechanism of recovery after stroke might be the key to answer these questions. In fact, it has been found that early increased UL practice does not necessarily mean better outcomes in neuroplasticity. In studies of rats, it was found that forced overuse of the affected limb 7 days (by casting the unaffected limb) after an induced stroke actually caused an expansion of the neural injury and interference in the restoration of affected limb function. Although it is always important to interpret results of animal studies with caution, the results show that there is a need for a greater understanding of the neuroplasticity mechanism behind early UL increased practice, otherwise we might possibly do more harm than good to stroke patients.

There is still a lack of studies investigating the neuroplastic reorganisation of increased UL practice during early post-stroke. Only one study has been found, thus far, on investigating the effect of early increased UL practice on neuroplasticity after stroke in humans. In this recent study by Hubbard et al, fMRI (functional magnetic resonance imaging) showed that stroke patients in the early increased training group showed increased activation in ipsilesional anterior cingulate and supplementary motor areas, and reduced activation in contralateral cerebellum, when compared to the standard care group. The increased activation of ipsilesional anterior cingulate and supplementary motor areas in the early increased training group was associated with early motor learning and attention, and the reduction in the activation of the contralateral cerebellum was interpreted as constituting better recovery in stroke patients.

Most studies investigated the effect of additional UL practice on neuroplasticity on patients of more than 3-months post-stroke and patients of chronic stroke (>6-months post-stroke). These studies did not include control groups of stroke patients without UL additional practice to compare their outcomes. If there was a control group in these studies, the controls were normal healthy subjects.

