Doctors, therapists and nurses who are taking care of the subjects in TTSRHC will be informed of the subjects' participation in SURE program and will be kindly requested to keep a look out of any verbal and non-verbal expressions of fatigue by the subjects. They will be informed to give similar advice by CPI to stop exercise and rest before continually or stop the exercises entirely if the subjects are too tired on that particular day. CPI will be informed by the treating team of their findings and will continue to monitor the subjects' suitability to continue with SURE program if there are reports of persistent fatigue due to self-exercises in the ward. Additional monitoring of fatigue level will be performed at pre, 2 weeks of intervention, post-intervention assessment using the Stanford Fatigue Scale.

A possible minimal risk is the development of allergy to the straps of the sensors. However, many research studies had used the sensors and there have been no reports of any adverse allergic reactions or problems reported with wearing the sensors.

Transcranial Magnetic Stimulation (TMS) Screening

TMS safety parameters have been documented and stimulation guidelines have been established (Wasserman, 1998). Seizures are the most important potential adverse event but are extremely rare. Mild headache, neck pain and discomfort from facial twitches are the most common and resolve spontaneously shortly after stimulation.

Exclusion criteria include pregnancy, presence of cardiac pacemakers, orthodontics (braces), metal implant and intracranial implants such as ventriculoperitoneal shunts and clips.

Functional Magnetic Resonance Imaging Investigation

Magnetic Resonance Imaging use radio waves similar to those used in radio and TV transmission. These have a much lower energy than X rays and are considered biologically safe. We follow strict safety guidelines which are designed to prevent the possible hazards of MRI: burns and electric shocks. The main risk in MRI is injury or death arising from the action of the strong magnetic field on any metal objects on or within the body. This may result in flying metal objects or damage to tissue. Strict screening procedures to remove external metal objects and exclude unsuitable volunteers will be carried out.

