Subjects' fatigue levels will be assessed using 0-10 point Stanford Fatigue Visual Numeric Scale (Stanford Patient Education Research Centre, n.d). Subjects' level of affected UL pain will be assessed using 0-10 rating Visual Analogue Scale (VAS). Subjects' UL spasticity level for biceps and finger flexors will be assessed using Modified Ashworth Scale (MAS). These assessments will be performed pre, 2 weeks in training, and post-training.

SURE program feasibility is also assessed by the compliance rate, dropout rate and any adverse events reported during the intervention period.

Subjects and their caregiver will be asked to fill up a questionnaire to rate on **SURE** program's ease, benefit and overall satisfaction based on VAS (rating 0 -10). In addition, 10 nurses in the ward who have taken care of the stroke patients undergoing the **SURE** program in the ward will also be asked to fill up a questionnaire to rate the ease, difficulty, advantages and disadvantages on **SURE** program implementation in the ward.

TMS Screening

A research staff will apply TMS to the subject. The subject will be seated comfortably and instructed to remain as still as he/ she can. A tight swim cap will be worn by the subject. The vertex will be marked on the cap. Single pulse TMS was delivered using a single Magstim 200 via the coil of figure of eight. The coil position was maintained manually by the assistant and the handle of the coil point to posterior with an angle of 45 degree to the sagittal plane. Surface electromyography (EMG) electrodes are attached to the extensor carpi radialis (ECR) for EMG recording. The "hot spot" of the motor evoked potential (MEP) from ECR is first identified and marked for affected side. This spot will be used for all recordings on that side. The subject will

be considered MEP positive if more than or equal 50 μ V amplitude can be elicited in 50% of 10 successive trials while the muscle is at rest. If this criterion is not met with stimuli delivered at maximal intensity, the subject will be considered MEP negative.

Multimodal MRI imaging and Analysis

MRI data acquisition

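### Section 9.1 defines serious and unanticipated events only by MRI cause, so a non-fatal serious event from TMS or SURE exercise, or a recurrent stroke, has no category and no clear reporting deadline

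*Protocol*

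**What the plan says.** Protocol section 9.1, headed as definitions, has four entries:

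- UPIRTSO: "Occurrence of epileptic seizures during fMRI investigations".
- Serious adverse event: "MRI related injury or death arising from the action of the strong magnetic field on any metal objects on or within the body".
- In the remaining class, for adverse events of other kinds, the first entry is burns and shocks caused by MRI.
- The second entry in that class is: "Development of allergy to the straps of the accelerometers".

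It gives no general criterion of seriousness and mentions neither TMS nor exercise.

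Section 2.4b sets out the risks by procedure. Under TMS screening it says: "Seizures are the most important potential adverse event but are extremely rare". It adds: "Mild headache, neck pain and discomfort from facial twitches are the most common". Its MRI text covers magnetic-field injury, burns, shocks, tissue heating, nerve stimulation and noise, but not seizure. Under the SURE program it names fatigue, asks subjects to log pain and fatigue, and mentions strap allergy.

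Section 9.2 sets two deadlines under a heading that names UPIRTSO events and SAEs: 24 hours for problems involving a local death, regardless of relatedness, and 7 calendar days for all remaining problems.

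Collection is worded more widely. Section 6 counts among the SURE feasibility measures the "compliance rate, dropout rate and any adverse events reported during the intervention period". Section 9.4 has a daily review of any possible adverse event, medical ones included. Section 6.3d monitors events during SURE and fMRI. Section 11.2b monitors adverse events and complaints daily.

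**The concern.** A definition of SAE normally turns on how serious the event is. Here it turns on one cause. The causes left out include the screening procedure whose main risk the protocol itself says is seizure, and the intervention that the trial exists to test. The reporting deadlines attach to the defined categories, so a serious event outside them may be seen, recorded and still have no stated route to the review board.

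What is at stake is consistent and timely safety reporting. Under 9.4 the CPI does the clinical safety monitoring. The CPI also delivers SURE and knows the allocation (sections 5 and 8.5). Without a general definition, whether a serious clinical event counts as an SAE rests on that one unblinded person's judgement.

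**Working it through.** No figure in the plan needs to be reproduced, because the point concerns the content of definitions. The check sets 9.1 and 9.2 beside the events that the protocol foresees or that its procedures make possible.

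| Event | Where the protocol foresees it | Category in 9.1 | Deadline in 9.2 |
|---|---|---|---|
| Local death, any cause | 9.2 | SAE only if from the magnetic field | 24 hours, whatever the cause |
| Non-fatal magnetic-field injury | 2.4b, MRI | SAE | 7 days |
| Seizure during fMRI | 9.1 only | UPIRTSO | 7 days |
| Non-fatal seizure during TMS | 2.4b, TMS | None | Unclear |
| Non-fatal recurrent stroke | 6.3b, during transport | None | Unclear |
| Serious non-fatal event in SURE exercise | Not specified; 2.4b names fatigue and pain | None | Unclear |

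**Step 1: what 9.1 covers.** Of its four entries, three concern MRI or fMRI and one concerns the accelerometer strap. Section 2.4b does list strap allergy under its SURE heading. However, it comes from the sensor, which section 6 says both groups wear, and not from the exercise.

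**Step 2: seizure.** Section 2.4b names four TMS events: seizure, headache, neck pain and facial-twitch discomfort. None has an entry in 9.1 when it occurs during TMS. Seizure appears in 9.1 only for fMRI, the procedure whose risk text omits it.

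**Step 3: exercise exposure.** Section 8.1 gives 24 additional hours. This reproduces: 1 hour × 6 days × 4 weeks = 24 hours, over 6 × 4 = 24 exercise days. Section 5 schedules CPI reviews at 3 + 3 + 2 + 1 = 9 over the four weeks. Even if each review falls on a different exercise day, 24 − 9 = 15 days have none. If the first teaching session and the next-day check in 2.4b are additional to the nine, the figure is 24 − 11 = 13. Practice continues at home after discharge. Ward staff or caregivers may be present, so the exercise is partly, not wholly, unsupervised.

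**Step 4: reach of the 7-day deadline.** The clause speaks of all other problems, which is wide. Its heading confines the timeline to UPIRTSO events and SAEs, which 9.1 makes narrow. Both readings are open for the last three rows of the table.

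**Step 5: whether other sections settle it.** Sections 6, 6.3d, 9.4 and 11.2b widen what is collected but define no category, and 9.4 sends the reader back to section 9. Neither 9.4 nor 6.3d names TMS. Section 6.3b says how an emergency in transit is handled and who tells the treating doctor, but not how the event is classified.

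**The case against.** Several points on the other side are sound.

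- **Collection is broad.** A reader might infer that SURE harms go unmonitored, or that a comparison of adverse events between groups would look clean because of the definitions. The protocol does not support this. The feasibility measure is any reported adverse event, daily review covers medical events, and pain, fatigue and spasticity are measured at three visits. The protocol also states no between-group comparison of adverse events. TMS is one visit before the intervention starts, so its gap cannot bear on such a comparison.
- **The stopping rule is independent of 9.1.** A reader might infer that an undefined event cannot stop the trial. Section 11.2c ties stopping to safety being compromised by study procedures, and TMS and SURE are both study procedures.
- **Section 9.1 need not be a closed list.** It does not say that it is, and 9.2 takes in unrelated deaths, which 9.1 does not. This stands as an ambiguity. But the section is headed as definitions and nothing marks its entries as examples.
- **The seizure entry can be read coherently.** UPIRTSO covers unanticipated problems. Seizure is disclosed for TMS and so anticipated there; in fMRI it would be unanticipated. This is a fair reading, so the entry is not plainly a mistake. It still leaves a TMS seizure without an SAE entry.
- **The background warning is limited.** The remark in section 1.1, "otherwise we might possibly do more harm than good to stroke patients", follows a study of rats forced to overuse the affected limb, and the text itself urges caution. It identifies no SURE event that 9.1 had to list.

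**Conclusion.** The point holds as a gap in classification and reporting. As written, a non-fatal serious event from TMS or SURE exercise, or a non-fatal recurrent stroke, has no defined category, and it is unclear whether the 7-day deadline applies. Local deaths are not affected.

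The size cannot be put as a number. The protocol gives no expected event rates and itself calls TMS seizures extremely rare, so few events may ever be touched. A count of listed event types would not measure events missed. With 20 patient subjects, though, the handling of a single serious event matters.

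The conclusion assumes that 9.1 is applied as worded and that the heading of 9.2 governs its deadlines. If the review board's own rules supply a general SAE definition, the practical gap shrinks, but this protocol neither states nor cites one. The change is worth making because it is cheap and removes a real inconsistency; it does not call the trial's analysis into question.

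**What to change.** Reconcile section 9.1 with 2.4b, 9.2 and 9.4:

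1. Define an SAE by seriousness, whatever the procedure or cause.
2. State that the MRI and strap events listed in 9.1 are examples.
3. Name TMS and SURE exercise as sources of reportable events in 9.1, and add TMS to the monitoring text in 9.4 and 6.3d.
4. Say in 9.2 whether the 7-day deadline covers every non-fatal serious event or only those in the defined categories.

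Tabulating events by group and labelling logged pain and fatigue as adverse events are optional. The first can be left to the analysis plan, and both symptoms are already measured.

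The cost is wording and a few more events to report. No visit or assessment is added, since review is already daily.
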